**Prior/Concurrent Clinical Study Experience**

12. Has participated in another investigational study within 4 weeks (or 5 half-lives of the investigational drug, whichever is greater) prior to the prestudy (screening) visit. The window will be derived from the date of the last visit in the previous study.

## Diagnostic Assessments

13. Has a mean QTc interval >450 msec, has a history of risk factors for Torsades de Pointes (eg, heart failure/cardiomyopathy or family history of long QT syndrome), has uncorrected hypokalemia or hypomagnesemia, is taking concomitant medications that prolong the QT/QTc interval.

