### **5 STUDY POPULATION**

In Part 1 male and female participants with moderate hepatic impairment and healthy participants between the ages of 18 and 75 years of age may be enrolled. If Part 2 is conducted, male and female participants with mild hepatic impairment between the ages of 18 and 75 will be enrolled.

The individual age and weight of the healthy participants is aimed to be within the range  $\pm$  15 years and  $\pm$  20% of the mean age and weight of participants with moderate hepatic impairment. In addition, the numbers of males and females of the healthy participants will be generally matched to the numbers of hepatic insufficient participants within  $\pm$  1; i.e., if there are 4 males and 4 females in the hepatic insufficient group, every effort will be made to ensure a 4:4 ratio in the healthy participants, but 3:5 or 5:3 would be acceptable as well.

Prospective approval of protocol deviations to recruitment and enrollment criteria, also known as protocol waivers or exemptions, is not permitted.

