#### **Type of Participant and Disease Characteristics**

1. Has a diagnosis of chronic (> 6 months), stable (no acute episodes of illness within the previous 2 months due to deterioration in hepatic function) hepatic impairment with features of cirrhosis due to any etiology.
2. Part 1 only: Has a score on the Child-Pugh scale ranging from 7 to 9 (moderate hepatic impairment) at screening. At least 4 (or at least 3 in the situation where only 6 participants are enrolled or complete the study) of the participants must have a score of 2 or higher on at least one of the laboratory parameters (i.e., albumin, INR, and bilirubin) at screening on the Child-Pugh scale.
3. Part 2 only: Patient's score on the Child-Pugh scale must range from 5 to 6 (mild hepatic impairment).
4. With the exception of hepatic impairment, is in generally good health based on medical history, physical examination, VS measurements and ECGs performed prior to randomization. Appendix 9 provides a table of the 12-Lead Electrocardiogram Abnormality Criteria. Participants with stable, chronic medical or psychiatric conditions may be included at the discretion of the investigator and the Sponsor.
5. With the exception of hepatic impairment, is in good health based on laboratory safety tests obtained at the screening visit and prior to randomization. Appendix 2 provides a table of laboratory safety tests to be performed. Appendix 10 provides an algorithm for the assessment of out of range laboratory values.
6. Has a  $BMI \geq 18.5$  and  $\leq 40 \text{ kg/m}^2$ . See Section 8.3.1 for criteria on rounding to the nearest whole number.  $BMI = \text{weight (kg)}/\text{height (m)}^2$ .

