#### **Medical Conditions**

1. Has a history of any illness that, in the opinion of the Investigator, might confound the results of the study or poses an additional risk to the participant by their participation in the study.
2. Is institutionalized or mentally or legally incapacitated at the time of prestudy (screening) visit or expected during the conduct of the study.
3. Has a history of cancer (malignancy).
4. Exceptions: (1) Adequately treated nonmelanomatous skin carcinoma or carcinoma in situ of the cervix or; (2) Other malignancies which have been successfully treated with appropriate follow up and therefore unlikely to recur for the duration of the study, in the opinion of the investigator and with agreement of the Sponsor (eg, malignancies which have been successfully treated  $\geq 10$  years prior to the prestudy [screening] visit).
5. Has a history of significant multiple and/or severe allergies (eg, food, drug, latex allergy), or has had an anaphylactic reaction or significant intolerance (ie, systemic allergic reaction) to prescription or non-prescription drugs or food.
6. Has known hypersensitivity to the active substance or any of the excipients of the study drug.
7. Is positive for HIV.
8. Had major surgery, donated or lost 1 unit of blood (approximately 500 mL) within 4 weeks prior to the prestudy (screening) visit.

9. Participant has an estimated CrCl  $\leq$  60 mL/min based on the CG Equation at Screening.

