## 8 STUDY ASSESSMENTS AND PROCEDURES

- Study procedures and their timing are summarized in the SoA.
- Adherence to the study design requirements, including those specified in the SoA, is essential and required for study conduct.
- The investigator is responsible for ensuring that procedures are conducted by appropriately qualified (by education, training, and experience) staff. Delegation of study site personnel responsibilities will be documented in the Investigator Trial File Binder (or equivalent).
- All study-related medical decisions must be made by an investigator who is a qualified physician.
- All screening evaluations must be completed and reviewed to confirm that potential participants meet all eligibility criteria. The investigator will maintain a screening log to record details of all participants screened and to confirm eligibility or record reasons for screening failure, as applicable.
- Procedures conducted as part of the participant's routine clinical management (eg, blood count) and obtained before signing of ICF may be utilized for screening or baseline purposes provided the procedure met the protocol-specified criteria and were performed within the time frame defined in the SoA.
- Additional evaluations/testing may be deemed necessary by the investigator and or the Sponsor for reasons related to participant safety. In some cases, such evaluation/testing may be potentially sensitive in nature (eg, HIV, Hepatitis C), and thus local regulations may require that additional informed consent be obtained from the participant. In these cases, such evaluations/testing will be performed in accordance with those regulations.

The maximum amount of blood collected from each participant over the duration of the study is outlined in Appendix 8.

Repeat or unscheduled samples may be taken for safety reasons or for technical issues with the samples.

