#### **8.3.4 Clinical Safety Laboratory Assessments**

Refer to Appendix 2 for the list of clinical laboratory tests to be performed and to the SoA for the timing and frequency.

- The investigator or medically qualified designee (consistent with local requirements) must review the laboratory report, document this review, and record any clinically relevant changes occurring during the study in the AE section of the CRF. The laboratory reports must be filed with the source documents. Clinically significant abnormal laboratory findings are those which are not associated with the underlying disease, unless judged by the investigator to be more severe than expected for the participant's condition.
- All protocol-required laboratory assessments, as defined in Appendix 2, must be conducted in accordance with the laboratory manual and the SoA.
- If laboratory values from nonprotocol-specified laboratory assessments performed at the institution's local laboratory require a change in study participant management or are considered clinically significant by the investigator (eg, SAE or AE or dose modification), then the results must be recorded in the appropriate CRF (eg, SLAB).
- For any laboratory tests with values considered clinically significantly abnormal during participation in the study or within 5 days after the last dose of study intervention, every attempt should be made to perform repeat assessments until the values return to normal or baseline or if a new baseline is established as determined by the investigator.

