## 10.2 Appendix 2: Clinical Laboratory Tests

- The tests detailed in [Table 5] will be performed by the local laboratory.
- Protocol-specific requirements for inclusion or exclusion of participants are detailed in Section 5 of the protocol.
- Additional tests may be performed at any time during the study as determined necessary by the investigator or required by local regulations.

Table 5 Protocol-required Safety Laboratory Assessments

Laboratory Assessments	Parameters			
Hematology	Platelet Count	RBC Indices: MCV MCH Reticulocytes	WBC count with Differential: Neutrophils Lymphocytes Monocytes Eosinophils Basophils	
	RBC Count			
	Hemoglobin			
	Hematocrit			
Chemistry	Blood Urea Nitrogen (BUN)	Potassium	Aspartate Aminotransferase (AST)/ Serum Glutamic-Oxaloacetic Transaminase (SGOT)	Total bilirubin (and direct bilirubin, if total bilirubin is elevated above the upper limit of normal)
	Albumin	Bicarbonate or Total CO 2	Chloride	Phosphorous
	Creatinine	Sodium	Alanine Aminotransferase (ALT)/ Serum Glutamic-Pyruvic Transaminase (SGPT)	Total Protein
	Glucose (fasting)	Calcium	Alkaline phosphatase	
Coagulation	• INR (International normalized ratio, for hepatic impaired participants only)			
Routine Urinalysis	• Specific gravity • pH, glucose, protein, blood, ketones, [bilirubin, urobilinogen, nitrite, leukocyte esterase] by dipstick • Microscopic examination (if blood or protein is abnormal)			
Other Screening Tests	• Follicle-stimulating hormone (as needed in women of nonchildbearing potential only) • Serum or urine alcohol and drug screen (to include at minimum: amphetamines, barbiturates, cocaine, opiates, cannabinoids and benzodiazepines). Alcohol breath test for alcohol screen is permitted. • Highly sensitive serum or urine human chorionic gonadotropin (β-hCG) pregnancy test (as needed for WOCBP) • Serology (HIV-1 and HIV-2 antibodies in all participants, HBsAg, and hepatitis C virus antibody in healthy participants only)			
NOTES: The investigator (or medically qualified designee) must document their review of each laboratory safety report.				

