## 10.10 Appendix 10: Algorithm for Assessing Out of Range Laboratory Values

For all laboratory values obtained at prestudy (screening) visit and/or predose evaluation:

- A. If all protocol-specified laboratory values are normal, the participant may enter the study.
- B. If a protocol specified laboratory value is outside of the parameter(s) outlined in the inclusion/exclusion criteria (including a repeat if performed), the participant will be excluded from the study.
- C. If  $\geq 1$  protocol-specified laboratory value not specified in the inclusion/exclusion criteria is outside the normal range, the following choices are available:
  1. The participant may be excluded from the study;
  2. The participant may be included in the study if the abnormal value(s) is NCS (the investigator must annotate the laboratory value “NCS” on the laboratory safety test source document).
  3. The participant may be included in the study if the abnormality is consistent with a pre-existing medical condition which is not excluded per protocol (eg, elevated eosinophil count in a participant with asthma or seasonal allergies), the medical condition should be annotated on the laboratory report.

OR

4. The abnormal test may be repeated (refer items a. and b. below for continuation of algorithm for repeated values).
  - a. If the repeat test value is within the normal range, the participant may enter the study.
  - b. If the repeat test value is still abnormal, the study investigator will evaluate the potential participant with a complete history and physical examination, looking especially for diseases that could result in the abnormal laboratory value in question. If such diseases can be ruled out, and if the abnormal laboratory value is not clinically relevant, then the participant may enter the study.
- D. If there is any clinical uncertainty regarding the significance of an abnormal value, the participant will be excluded from the study.

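### Hypomagnesemia is a mandatory exclusion, but no required screening or predose test measures magnesium

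*Combined protocol and SAP*

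**What the plan says.** Criterion 11 (Section 5.2.1) and criterion 13 (Section 5.2.2), both under the Diagnostic Assessments subheading, share the same electrolyte wording. A participant must be excluded who "has uncorrected hypokalemia or hypomagnesemia, is taking concomitant medications that prolong the QT/QTc interval".

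The list of laboratory work that has to be done is Appendix 2, Table 5. Section 8.3.4 states: "All protocol-required laboratory assessments, as defined in Appendix 2, must be conducted in accordance with the laboratory manual and the SoA". The good-health inclusion criteria point to the same place (criterion 2 for healthy participants, criterion 5 for hepatic participants): "Appendix 2 provides a table of laboratory safety tests to be performed".

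The Table 5 chemistry panel is legible and complete. It includes potassium, sodium, chloride, calcium and phosphorous, but not magnesium.

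Section 8 requires that "All screening evaluations must be completed and reviewed to confirm that potential participants meet all eligibility criteria", and Section 5 closes off exceptions: "Prospective approval of protocol deviations to recruitment and enrollment criteria, also known as protocol waivers or exemptions, is not permitted".

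**The concern.** Two electrolyte deficits are named together as reasons for exclusion. One is measured in everybody, twice, before dosing. The other is measured in nobody unless an investigator chooses to order it. The magnesium condition then rests on history or discretion, and because this is a multi-site study, two sites could handle it differently while both follow the protocol to the letter.

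What is at stake is the cardiac-safety screen. The condition belongs to a QT/Torsades criterion whose other parts all have a planned assessment: QTc by triplicate ECG at screening and predose, potassium by chemistry, Torsades risk factors by medical history, and QT-prolonging drugs by medication review. The gap matters most in the hepatic groups, where Section 6.5 allows diuretics. Footnote c of Appendix 11 already recognises potassium imbalance as an adverse effect to be managed when ascites is treated; the documents do not discuss magnesium in that setting.

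No pharmacokinetic estimate or interval is at stake.

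**Working it through.** The plan states no figure on this point, so the check is a cross-tabulation and not a calculation.

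**Step 1. Is magnesium required anywhere?** Table 5, both Schedules of Activities (1.3.1 and 1.3.2, with their footnotes) and the site-specific requirements in Appendix 7 were read for any magnesium test. There is none. In the Schedules, the laboratory row at screening and predose is the hematology, urinalysis and chemistry panel, which refers back to Section 8.3.4 and Appendix 2. Magnesium appears in the documents only through the word *hypomagnesemia* in criteria 11 and 13.

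**Step 2. Is this typical of the protocol or an isolated omission?** Each condition in Sections 5.1 and 5.2 that turns on a named laboratory test was matched to Table 5.

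| Test needed | Healthy (criterion) | Hepatic (criterion) | In Table 5? |
|---|---|---|---|
| HBsAg | Excl. 6 | – | Yes |
| Hepatitis C antibody | Excl. 6 | – | Yes |
| HIV | Excl. 6 | Excl. 7 | Yes |
| Creatinine (for CrCl) | Excl. 8 | Excl. 9 | Yes |
| Potassium | Excl. 11 | Excl. 13 | Yes |
| **Magnesium** | **Excl. 11** | **Excl. 13** | **No** |
| Drug screen | Excl. 16 | Excl. 17 | Yes |
| Alcohol test | – | Excl. 17 | Yes |
| Pregnancy test | Incl. 6 | Incl. 8 | Yes |
| Bilirubin, albumin, INR (Child-Pugh) | – | Incl. 2/3 | Yes (all 3) |

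- Healthy: 3 (serology) + 1 (creatinine) + 2 (electrolytes) + 1 (drug screen) + 1 (pregnancy) = 8 conditions, 7 with a listed test.
- Hepatic: 3 (Child-Pugh) + 1 (HIV) + 1 (creatinine) + 2 (electrolytes) + 2 (drug and alcohol) + 1 (pregnancy) = 10 conditions, 9 with a listed test.

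The general good-health criterion and FSH are left out because Sections 5.1 and 5.2 name no analyte for them. Pooling both groups, counting each test once and including FSH gives 13 conditions, 12 with a listed test. Either way the only one unmatched is magnesium.

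**Step 3. Does the wording confine the exclusion to known cases?** Where the protocol means that, it says so: "Has known hypersensitivity to the active substance or any of the excipients of the study drug". The Torsades condition in the same sentence is expressly framed as a history. The electrolyte condition carries neither qualifier, and its paired electrolyte is measured.

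**Step 4. Does Appendix 10 fill the gap?** Rule B excludes a participant "If a protocol specified laboratory value is outside of the parameter(s) outlined in the inclusion/exclusion criteria". It acts on laboratory values the protocol specifies. Magnesium is not one of them, so the rule has nothing to act on. Appendix 10 does not waive the exclusion; it simply never reaches it.

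**The case against.** The best reply is that the criterion works without a mandated assay. *Uncorrected* can be read as describing a recognised deficit that has not been repleted. Many eligibility conditions are settled by history or physician judgement, and confirming all criteria does not mean one assay per criterion. Investigators also have routes to testing. Appendix 2 says: "Additional tests may be performed at any time during the study as determined necessary by the investigator or required by local regulations". Section 8 lets earlier routine results serve for screening, Section 8.10.6 lets safety tests be added to blood already drawn, and any investigator safety concern is itself exclusionary.

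The practical risk is also limited. QTc is measured directly and a mean above 450 msec excludes. Exposure is a single 4 mg dose, half of the highest well-tolerated starting dose of 8 mg (Section 4.3). Section 2.2.2.2 reports no clinically meaningful drug-related ECG changes in the completed Phase 1 studies. The tally of matched conditions describes the protocol's consistency, not the risk to a participant.

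Most of this stands, and it is why the point is minor. It does not remove the gap. Permission to test is not a requirement, and the known-cases reading sits badly beside a paired electrolyte that is measured at both time points.

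A further objection concerns the remedy. The criteria give no magnesium cutoff, so a low result might be argued to fall under Appendix 10 rule C, where the investigator can call it not clinically significant and enrol. Rule C, however, covers values not specified in the eligibility criteria, and low magnesium is named there, so rule B is the better reading. The missing cutoff is real, but it applies equally to potassium today.

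**Conclusion.** The concern holds. Criteria 11 and 13 make uncorrected hypomagnesemia a mandatory exclusion, and nothing in the required screening or predose tests would detect an unrecognised case. It is the single unmatched laboratory-based condition in each eligibility list (1 of 8 healthy, 1 of 10 hepatic). A site following the plan exactly could dose someone the plan says must be excluded.

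The consequence is confined to safety screening. AUC0-inf, Cmax and interval precision are unaffected. The documents give no prevalence of hypomagnesemia, so no number of affected participants or extra screen failures is claimed. The conclusion assumes that Appendix 2 is the operative list, as Section 8.3.4 says; the laboratory manual mentioned there is not among the documents. The change is worth making because it is cheap and makes a stated exclusion verifiable.

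**What to change.** Add serum magnesium to the Table 5 chemistry list, measured at screening and on the predose safety sample. Footnote a of both Schedules already requires predose safety results to be reviewed before allocation, and Appendix 10 rule B would then apply. As the criteria give no number for either electrolyte, it would help to state that both are read against the local laboratory's lower limit of normal; that would also settle the choice between rules B and C.

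The cost is one extra assay on two samples per participant that are already drawn. For the planned maximum of 16 + 8 = 24 participants that is 24 × 2 = 48 assays, plus one for each person screened but not enrolled. No new visit is needed. Section 8.10.6 already foresees adding safety tests to drawn blood, and if more volume were needed, Appendix 8 allows up to 75 mL extra. The remaining cost is a possible extra screen failure, which could slow recruitment somewhat in hepatic groups of 6 to 8.

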## Other Exclusions

14. Is under the age of legal consent.
15. Does not agree to follow the smoking restrictions as defined by the CRU.
16. Consumes excessive amounts, defined as greater than 6 servings (1 serving is approximately equivalent to 120 mg of caffeine), of coffee, tea, cola, energy drinks, or other caffeinated beverages per day.
17. Is a regular user of cannabis, any illicit drugs or has a history of drug abuse within approximately 3 months. Participants must have a negative alcohol test and with the exception of cannabis, participants must have a negative UDS prior to randomization. Participants with hepatic impairment may be allowed for inclusion with a positive UDS for opiates or benzodiazepines if they have an active prescription from a licensed health care provider.
18. Is unwilling to comply with the study restrictions (see Section 5.3 for a complete summary of study restrictions).
19. Presents any concern by the investigator regarding safe participation in the study or for any other reason the investigator considers the participant inappropriate for participation in the study.
20. Is or has an immediate family member (eg, spouse, parent/legal guardian, sibling, or child) who is investigational site or Sponsor staff directly involved with this study.

## 5.3 Lifestyle Considerations

### 5.3.1 Meals and Dietary Restrictions

#### 5.3.1.1 Diet Restrictions

In each treatment period, participants will fast from all food and drinks, except water, for at least 8 hours before study drug administration. Participants will fast from all food and drinks except water between study drug administration and the first scheduled meal. Meals and snack(s) will be provided by the investigator at time points indicated in the study flowchart. Participants will fast from all food and drinks except water between meals and snacks. After the 24-hour postdose procedures have been completed, subsequent meals and snacks will be unrestricted in caloric content, composition, and timing.

Water will be provided during study drug administration. Water will be restricted 1 hour before and 1 hour after study drug administration.

### **5.3.1.2 Fruit Juice Restrictions**

Participants will refrain from the consumption of grapefruit juice, grapefruits, and grapefruit products beginning approximately 2 weeks prior to administration of the initial dose of study drug, throughout the study until the last PK sample is collected.

Participants also will refrain from the consumption of all fruit juices 24 hours prior to and after study drug administration. On all other days during the study, consumption of fruits and fruit juices (except for grapefruit, grapefruit juices, and grapefruit products) is allowed.

